Research Protocol

Protocol Title:

Early Stability of Short Implants with Shallow Threads in the
Posterior Mandible: A Controlled Clinical Pilot Study.

Date: August - 19- 2025

Principal Investigator

[name]

Thesis Supervisor:

[name] [name]

(Associate Professor of Oral and Maxillofacial Surgery)

University of Science and Technology,

Yemen.

1. Background and Rationale

Patients with severely resorbed posterior mandibles face a significant challenge. While short implants (SHI, $\leq 8\text{mm}$) offer a less invasive alternative to complex bone augmentation, they are associated with a higher risk of early failure, often linked to compromised stability during the critical healing phase known as the "stability dip." This dip, a period of osteoclast-mediated resorption, creates micromotion that can disrupt osseointegration. The role of implant macrodesign, specifically shallow threads, and bone density in modulating this early stability trajectory remains unclear. This study aims to prospectively compare the early stability dynamics of short (7mm) versus standard (11mm) shallow-threaded implants to provide evidence for their use as a viable graft-less solution.

2. Study Objectives and Hypotheses

· Primary Objective:

To compare the early stability dynamics (primary stability, stability dip, and onset of secondary stability) of 7 mm short implants (SHI) versus 11 mm standard implants (SDI), both with an identical shallow-threaded macrodesign, in the non-augmented posterior mandible over 4 weeks.

· **Secondary Objective:**

To assess the effect of bone density (D2 vs. D3) on these stability parameters.

Hypotheses:

- H_01 : No significant difference in primary stability (ITV, ISQ-T0) exists between SHI and SDI.
- H_02 : No significant relationship exists between baseline ISQ and the stability dip magnitude/duration for either implant type.
- H_03 : Bone density has no differential effect on stability parameters between SHI and SDI.

3. Study Design

A prospective, controlled, non-randomized clinical pilot study employing $\geq 80\%$ split-mouth design where anatomically feasible. Implant allocation follows clinical necessity principles:

- Short Implant (SHI; 7 mm): Sites with 8–10 mm bone height above the inferior alveolar canal.
- Standard Implant (SDI; 11 mm): Sites with >10 mm bone height. Randomization is precluded on ethical grounds, as placing an SHI in a site suitable for an SDI violates the standard of care.

4. Participant Selection

· Inclusion Criteria:

- Aged 18–65 years.
- Posterior mandibular partial edentulism requiring implant placement.
- Native bone height of 8–13 mm above the inferior alveolar canal.
- Bone width ≥ 5.5 mm.

- Bone density classified as D2 (850–1250 HU) or D3 (350–850 HU) via pre-operative CBCT.
- Plaque Index ≤ 1 .
- ASA physical status I or II.
- Provides written informed consent.

- **Exclusion Criteria:**
- Absolute surgical contraindications.
- Uncontrolled diabetes (HbA1c $> 7\%$) or immunosuppression.
- History of head/neck radiation or bisphosphonate therapy.
- Active periodontitis (PPD > 5 mm) or bone pathology.
- Smoking > 10 cigarettes/day.
- Parafunctional habits.
- Previous bone grafting at the intended implant site.

5. Sample Size

The sample will consist of Ten participants receiving 20 implants (10 SHI, 10 SDI). This is a pilot feasibility sample, determined by strict eligibility criteria and a post-hoc power analysis indicating 80% power to detect a clinically significant difference in ISQ dip ($\Delta\text{ISQ} \geq 5$) with an alpha of 0.05.

6. Materials and Methods

• **Implant System:**

A tiologic TWINFIT implants (DENTAURUM GmbH). Both SHI (7mm) and SDI (11mm) share an identical design:

- 4.2mm diameter
- 5-degree taper
- Shallow threads (0.35-0.45mm),
- Sandblasted, acid-etched (SLA) surface.

· Key Equipment:

- CBCT Machine (Vatech EZ-3D) for pre-surgical planning and bone density assessment.
- Surgical motor (W&H Implantmed) with a 20:1 reduction handpiece.
- Calibrated torque wrench.
- Resonance Frequency Analysis (RFA) device (Penguin RFA) with type 4 SmartPegs.

7. Study Procedures

· Pre-Operative Phase:

1. Screening against inclusion/exclusion criteria.
2. Clinical examination and plaque index recording.
3. CBCT scan with Hounsfield Unit (HU) calibration using a hydroxyapatite phantom to determine bone density (D2/D3).
4. Obtaining written informed consent.

· Surgical Protocol:

1. Premedication: Ibuprofen 400 mg.
2. Asepsis with povidone-iodine (perioral) and chlorhexidine (intraoral).
3. Local anesthesia (2% lidocaine with 1:80,000 epinephrine).
4. Crestal incision and full-thickness flap elevation.
5. Osteotomy performed with an under-preparation protocol.
6. Implant placement with slow manual seating. Insertion Torque Value (ITV) is recorded during the final 90° rotation.
7. SmartPeg attachment and baseline Implant Stability Quotient (ISQ) measurement using RFA (T0).
8. Closure with sutures.

· Post-Operative Care:

- Analgesics (Diclofenac) and antibiotics (Amoxicillin/Clavulanate).
- Instructions for soft diet and chlorhexidine mouth rinses.

- **Follow-up and Stability Monitoring:**

- Participants will return for ISQ measurements at the end of weeks 1, 2, 3, and 4 (T1, T2, T3, T4).
- At each visit, quadruple RFA measurements (buccal, lingual, mesial, distal) will be taken, and the mean ISQ value calculated.

8. Outcome Measures

- **Primary Stability:**

- Insertion Torque Value (ITV) in Ncm.
- Baseline ISQ value (T0).

- **Stability Dip Characteristics:**

- Dip Magnitude (Δ ISQ-min): Difference between ISQ at T0 and the lowest ISQ value (ISQ-min) recorded between T1-T4.
- Time of Dip (T-min): The week (T1-T4) at which the lowest ISQ value occurred.

- **Secondary Stability Onset:** The first timepoint where ISQ values consistently increase by ≥ 2 units from the ISQ-min.
- **Effect Modifier:** Bone density (D2 vs. D3) as a primary covariate.

9. Data Management and Statistical Analysis

- **Data Collection:**

De-identified data will be recorded on standardized Case Report Forms (CRFs) and stored in a password-protected electronic database (Excel).

- **Statistical Analysis:**

Will be performed using SPSS Statistics (v28). Analysis will include:

- Descriptive statistics for all variables.
- Paired t-tests (for bilateral cases) and independent samples t-tests (for full dataset) to compare primary stability (H_01).
- Pearson/Spearman correlation to assess the relationship between baseline ISQ and dip magnitude (H_02).
- Linear Mixed Models (LMM) to analyze longitudinal ISQ trajectories.

- Two-Way ANOVA to test the interaction effect of Implant Type and Bone Density on dip magnitude (H_03).
- A p-value of <0.05 will be considered statistically significant, with Bonferroni correction for multiple comparisons.

10. Ethical Considerations

- **Approval:**

This study has been approved by the University of Science and Technology Institutional Review Board. (IRB Approval No: **1447/0062/UREC/UST**).

- **Informed Consent:**

Written informed consent will be obtained from all participants after a detailed explanation of the study procedures, potential risks, and benefits.

· Confidentiality:

All participant data will be de-identified and stored securely. Access will be limited to the research team.

· Risk Management:

The study follows the ALARA principle for radiation. All surgical procedures will adhere to standard clinical protocols to minimize risks. An adverse event reporting plan is in place.

11. Dissemination Plan

The results of this study will be presented in the candidate's Master's thesis and submitted for publication in a peer-reviewed international journal in the field of oral implantology. Findings may also be presented at relevant scientific conferences.

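### H_02 is left to a plain correlation that is neither fixed as per-type nor as pooled; each reading has a cost, and one model on all implants would serve better

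*Protocol*

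**What the plan says.** - Section 2, H_02: "No significant relationship exists between baseline ISQ and the stability dip magnitude/duration for either implant type". The primary objective in the same section is comparative: "To compare the early stability dynamics (primary stability, stability dip, and onset of secondary stability"), for 7 mm against 11 mm implants.
- Section 9 ties one method to H_02: "Pearson/Spearman correlation to assess the relationship between baseline ISQ and dip magnitude (H_02"). It does not mention a split by type, an implant-type term or a participant effect. The linear mixed model in that section is for ISQ trajectories and is not linked to H_02. The only interaction named is implant type by bone density, for H_03.
- Section 5 gives the sample as "Ten participants receiving 20 implants (10 SHI, 10 SDI"). Section 3 plans at least 80% "split-mouth design where anatomically feasible", so the two sets of ten come largely from the same patients.
- Section 8 defines dip magnitude as "Difference between ISQ at T0 and the lowest ISQ value (ISQ-min) recorded between T1-T4".
- Section 9 also says: "A p-value of <0.05 will be considered statistically significant, with Bonferroni correction for multiple comparisons".

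**The concern.** The wording of H_02 points towards one correlation in the short implants and one in the standard implants; the wording of Section 9 fits a single correlation on all 20 just as well. The analyst can choose after seeing the data, and neither choice is sound. Two tests of ten implants are weak and will often disagree by chance. In a study that compares the two lengths, such a split could easily be reported as a difference between them. One test of 20 treats paired implants as independent and lets any difference between the arms in T0 and dip show up as a relationship between T0 and dip. Allocation follows bone height and H_01 itself asks whether T0 differs by type, so equal arms cannot be taken for granted.

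**Working it through.** **The plan's own figure.** Section 5 reports a "post-hoc power analysis indicating 80% power to detect a clinically significant difference in ISQ dip" of at least 5 ISQ units. This concerns the difference between types, not H_02. No SD is given, so it cannot be reproduced: 80% needs an SD of 3.77 (independent t-test, 10 per type) or an SD of differences of 5.02 (10 pairs). No power is stated for H_02.

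**Inputs.** From the protocol: 10 SHI, 10 SDI, alpha 0.05. Assumed: two-sided tests, bivariate normal data, a range of true correlations ρ, and within-patient correlation of 0 or 0.5 in both T0 and the residual part of dip.

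**Critical values.** r = t/√(n − 2 + t²).
- n = 10: 2.306/√(8 + 5.318) = 0.632
- n = 20: 2.101/√(18 + 4.414) = 0.444

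**Reading 1: per type.** Power p per type is simulated with the same ρ in both types. For independent sets, the chance that exactly one is significant is 2p(1 − p); at ρ = 0.5 this is 2 × 0.327 × 0.673 = 0.44.

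| True ρ, same in both | Power per type | Exactly one significant, independent | Same, within-patient correlation 0.5 |
|---|---|---|---|
| 0.3 | 0.13 | 0.23 | 0.21 |
| 0.4 | 0.21 | 0.33 | 0.29 |
| 0.5 | 0.33 | 0.44 | 0.38 |
| 0.6 | 0.48 | 0.50 | 0.42 |
| 0.7 | 0.68 | 0.44 | 0.38 |
| 0.8 | 0.87 | 0.23 | 0.20 |

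Outside this range the figure is smaller: 0.09 at ρ = 0 and 0.03 at ρ = 0.9 (independent sets). At a Bonferroni level of 0.025 the peak stays near 0.50 but moves to ρ of about 0.65 to 0.7.

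**Reading 2: pooled.** With no true relationship within types:
- Pairing alone (within-patient correlation 0.5, no arm difference): type I error 0.078.
- Arm differences alone, d₁ SD in T0 and d₂ SD in dip: pooled r = (d₁d₂/4)/√[(1 + d₁²/4)(1 + d₂²/4)]. For 1 SD in both, 0.25/1.25 = 0.20; for 1.5 SD in both, 0.5625/1.5625 = 0.36. Simulated rejection rates at n = 20 are about 0.14 and 0.37–0.38.

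**What one model gives.** A common slope adjusted for type on all 20 implants has power of about 0.61 and 0.81 at ρ = 0.5 and 0.6 (implants treated as independent), against 0.33 and 0.48 per type. A contrast between two correlations of n = 10 has standard error √(1/7 + 1/7) = 0.535 on the Fisher z scale. Power of 80% then needs a difference of 2.80 × 0.535 = 1.50, roughly r = 0 against 0.90.

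**Coupling.** Dip is T0 minus ISQ-min. If the two have equal variance and correlation k (assumption), corr(T0, dip) = √[(1 − k)/2]: 0.71 at k = 0, 0.50 at k = 0.5, 0.39 at k = 0.7 and 0.22 at k = 0.9. A non-zero correlation therefore arises by construction, whichever reading is used.

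**The case against.** - **Separate testing is not fixed.** A reader might infer from H_02 that the correlations are run type by type. Section 9 does not say so, and the choice could be settled in an analysis plan that is not shown. This stands, so the point cannot be that the protocol commits to two tests of ten. What remains is that the one method named, a plain correlation, is poor under either reading.
- **H_02 asks for no contrast between lengths.** It states a null for either type, not equality of the two relationships, and where the protocol does ask about effect modification (H_03) it names an interaction test. This also stands. A missing interaction does harm only if the two verdicts are read as a contrast.
- **Discordance half the time is a ceiling.** A reader might take 50% as the typical rate. It is the maximum of 2p(1 − p), reached near ρ = 0.6 with independent sets. The protocol gives no ρ, and pairing lowers the rate.
- **The arm shifts are assumed, and 0.20 and 0.36 lie below 0.444.** The shifts are indeed assumptions. The second half does not clear the pooled test: 0.20 and 0.36 are the centres about which sample correlations scatter, and the false-positive rate rises to the figures shown.
- **A common slope of dip on T0 would partly detect coupling.** Correct. The higher power of a common slope must not be sold as evidence about biology, and the fix has to deal with this.
- **The model is ambitious for 20 values in a pilot.** True of the interaction, which is why it is to be reported as an estimate only.

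**Conclusion.** The point holds as a modest, inexpensive improvement. Section 9 leaves H_02 to a naive correlation with its unit of analysis unspecified. Per type, power is 33–68% for ρ of 0.5 to 0.7, and verdicts disagree in about 23–50% of studies for a common ρ of 0.3 to 0.8 (about 20–42% with within-patient correlation 0.5). Pooled, type I error is about 0.08 from pairing alone and about 0.14 or 0.37–0.38 from assumed arm shifts of 1 or 1.5 SD. These sizes rest on normality, two-sided 0.05 and the assumed ρ, within-patient correlation and shifts; the protocol supplies none of the last three. The documents do not show that H_02 will be tested separately, that it claims a contrast between lengths, or that discordance of one half is to be expected in general.

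**What to change.** In Section 9, replace the H_02 correlation with one model on all implants: T0 centred within implant type, implant type, their interaction, and a participant effect. Report the common slope and the interaction as estimates with confidence intervals. Claim a difference between SHI and SDI only from the interaction. Show per-type slopes with intervals but without separate significance verdicts, and reword H_02 to match.

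Deal with the coupling openly, in one of two ways:

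1. Model ISQ-min on T0 and compare the slope with 1. Since dip = T0 − ISQ-min, the slope for dip is 1 minus this slope, so the test is algebraically the same as a zero slope for dip. It makes the coupling visible but does not remove it, and the report must say that measurement error and regression to the mean pull the slope below 1.
2. Use a coupling-corrected method, such as dip against the mean of T0 and ISQ-min. Their covariance is half the difference of the two variances, so it is zero when the variances are equal.

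Cost: a rewording of H_02 and one line of Section 9, with no new data; the mixed-model framework is already named there. The downside is a wide interval for the interaction with 10 versus 10 implants.

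### The bone-height threshold for the 11 mm implant (above 10 mm) is lower than the implant is long, so the written rule allows zero or negative clearance to the canal

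*Protocol*

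**What the plan says.** Section 3 (Study Design) forms the two groups by bone height, not by randomization. The short-implant rule reads "Short Implant (SHI; 7 mm): Sites with 8–10 mm bone height above the inferior alveolar canal". The standard-implant rule reads "Standard Implant (SDI; 11 mm): Sites with >10 mm bone height". The second line does not repeat the reference point, but the first line does, and so does the inclusion criterion in Section 4: "Native bone height of 8–13 mm above the inferior alveolar canal". The same measure is plainly meant throughout.

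Section 6 (Implant System) confirms the two lengths: "Both SHI (7mm) and SDI (11mm) share an identical design". Section 7 (Surgical Protocol) describes seating only as "Implant placement with slow manual seating" and gives no level relative to the bone crest.

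Four general provisions bear on the point:
- Section 3 introduces the allocation with "Implant allocation follows clinical necessity principles".
- Section 4 lists "Absolute surgical contraindications" among the exclusions.
- Section 6 lists a "CBCT Machine (Vatech EZ-3D) for pre-surgical planning and bone density assessment".
- Section 10 commits surgery to usual clinical practice so as to limit risk.

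None of them gives a distance to be kept from the canal.

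**The concern.** An implant needs at least its own length of bone above the canal, unless part of it is left above the crest. A cut-off of 10 mm for an 11 mm implant does not secure that. The short-implant rule sets its lower limit above the implant length, so the two rules are not built on the same principle.

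Two things are at stake. The first is safety: taken at face value, the rule sends some eligible sites to an implant that would reach or pass the canal. The second is the clarity of the allocation. The study is not randomized, so the height rule is what defines the arms. Section 3 also justifies not randomizing by saying that a short implant should not be given where a standard one would be suitable, and the 10 mm cut-off is the only numeric marker of suitability in the protocol. A surgeon with a 10.5 mm site therefore has no stated course: the rule points to an implant longer than the bone, and using the short implant departs from the rule.

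**Working it through.** **Inputs.** Standard implant: length 11 mm, threshold above 10 mm (Sections 3 and 6). Short implant: length 7 mm, heights 8 to 10 mm (Sections 3 and 6). Eligible heights: 8 to 13 mm (Section 4). Seating level and the resolution of height readings are not stated, so each is varied below as an assumption.

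**Step 1: full seating in bone, heights read finer than 1 mm.** Clearance = bone height − implant length.

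| Implant | Height (mm) | Clearance (mm) |
|---|---|---|
| Short | 8 | 8 − 7 = +1 |
| Short | 10 | 10 − 7 = +3 |
| Standard | 10.1 | 10.1 − 11 = −0.9 |
| Standard | 10.5 | 10.5 − 11 = −0.5 |
| Standard | 10.9 | 10.9 − 11 = −0.1 |
| Standard | 11 | 11 − 11 = 0 |
| Standard | 12 | 12 − 11 = +1 |
| Standard | 13 | 13 − 11 = +2 |

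The standard-implant window is 13 − 10 = 3 mm wide. Its first millimetre gives negative clearance. Its second (11 to under 12 mm) gives less than the minimum of the short-implant rule. Only from 12 mm up is that minimum met.

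**Step 2: vary the seating.** If x mm of the implant stays above the crest, clearance = height − (11 − x), which is negative for heights above 10 and below 11 − x.
- x = 0: negative from 10 to 11 mm.
- x = 0.5: negative from 10 to 10.5 mm.
- x = 1: no negative zone. Clearance is then only just above zero at the bottom of the range, and 11 − 1 = 10 mm of implant is in bone.

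**Step 3: vary the resolution (full seating).** If heights are recorded in whole millimetres, the lowest value above 10 is 11, with nominal clearance 0. If those values are rounded to the nearest millimetre, a recorded 11 covers true heights from 10.5 to under 11.5 mm, so true clearance runs from 10.5 − 11 = −0.5 to under 11.5 − 11 = +0.5 mm.

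**Step 4: the threshold needed.** At full seating, clearance of at least 0 needs a height of at least 11 mm. Matching the short-implant minimum of 8 − 7 = 1 mm needs 11 + 1 = 12 mm.

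**The case against.** The strongest reply is that an allocation rule is not an order to place. Section 3 divides sites between arms under clinical necessity, and being within the eligible height range is necessary but not sufficient for treatment. A site too short for its implant can reasonably be excluded as surgically contraindicated, and planning on CBCT would bring it to light. That stands as far as it goes: literal placement is unlikely. But these provisions are generic. They state no clearance and do not correct the number.

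A second reply is that negative clearance needs two conditions that the protocol does not state, full seating and sub-millimetre heights. That also stands, and the conclusion is conditional on both. Relaxing them shrinks the defect without yielding a sound rule. Leaving 1 mm above the crest only just avoids a negative value, and whole-millimetre heights still give zero nominal clearance at 11 mm.

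Two stronger readings are tempting. A reader might infer that participants will receive implants reaching into the canal. The documents do not support this, because of the safeguards above and because nothing says how many sites fall between 10 and 11 mm. A reader might also infer that the comparison of ISQ or insertion torque is biased by this threshold. That is not shown. If the too-short sites are simply excluded, every short implant still lies at 8 to 10 mm and every standard implant above 10 mm, so Section 3 still describes the arms. It would fail to do so only if such sites were given the 7 mm implant, and the protocol does not say that they are. The difference in bone height between the arms is a separate matter, present under any allocation by height.

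**Conclusion.** The point holds in a limited form. The threshold for the 11 mm implant is set below the implant's length and is wrong as a safety and allocation rule. With full seating and heights read finer than 1 mm, eligible sites above 10 and below 11 mm are assigned an implant longer than the bone above the canal, by more than 0 and less than 1 mm. With whole-millimetre heights the shortfall becomes zero nominal clearance at 11 mm. The short-implant rule leaves 1 to 3 mm.

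The number of affected sites cannot be found from the protocol, literal placement is unlikely, and no effect on the ISQ or insertion-torque results is claimed. The point should be fixed before recruitment relies on the rule: the number is safety-relevant and stated wrongly, which is different from a detail left for another document.

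**What to change.** In Section 3, set the standard-implant threshold to 11 mm plus a minimum canal clearance chosen by the clinical team. A threshold of 12 mm or more is one example. It would match the 1 mm that the short-implant rule leaves, although the protocol does not call that 1 mm a safety margin. Moving the threshold only to above 11 mm would not be enough: a site of 11.1 mm would have 11.1 − 11 = 0.1 mm.

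State what happens to sites between 10 mm and the new threshold. Either they receive the short implant, with Section 3 saying that they count as not suitable for the standard one, or they are excluded. This is a clinical choice that the documents do not settle. Record the CBCT height of each site on the CRF, so that the rule can be checked against what was done.

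The cost is a short amendment, with ethics review because approval is already in place, and a narrower window for the standard implant. At 12 mm or more the window is 13 − 12 = 1 mm, instead of 13 − 10 = 3 mm, of the eligible 13 − 8 = 5 mm: a cut of two thirds. With 10 standard implants needed and at least 80% split-mouth intended, sites for the standard implant and split-mouth pairs become clearly harder to find.

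### Ten participants not yet enrolled are justified partly by a post-hoc 80% power with no stated basis, and the SHI v SDI dip contrast it most naturally refers to has no hypothesis and no explicitly assigned test

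*Protocol*

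**What the plan says.** Section 5 describes a future sample: "The sample will consist of Ten participants receiving 20 implants (10 SHI, 10 SDI"). It gives two grounds for the number. The first is feasibility: "This is a pilot feasibility sample, determined by strict eligibility criteria". The second is "a post-hoc power analysis indicating 80% power to detect a clinically significant difference in ISQ dip", with a threshold of 5 ISQ and alpha 0.05. No SD, source data, test, sidedness or pairing is given.

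The primary objective in Section 2 has three parts: "To compare the early stability dynamics (primary stability, stability dip, and onset of secondary stability) of 7 mm short implants (SHI") against 11 mm standard implants (SDI). The hypotheses are narrower:

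- H_01: "No significant difference in primary stability (ITV, ISQ-T0) exists between SHI and SDI".
- H_02 relates baseline ISQ to the dip for each implant type.
- H_03 concerns whether bone density acts differently in the two types.

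Section 3 plans at least 80% "split-mouth design where anatomically feasible". Section 8 defines dip magnitude for a single implant: "Difference between ISQ at T0 and the lowest ISQ value (ISQ-min) recorded between T1-T4".

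Section 9 assigns "Paired t-tests (for bilateral cases) and independent samples t-tests (for full dataset) to compare primary stability (H_01"), a correlation to H_02, linear mixed models to ISQ trajectories over time, and a two-way ANOVA on dip magnitude to the type-by-density interaction (H_03).

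**The concern.** There are two linked defects.

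**The power statement does not work as a justification.** Post-hoc power is computed after the event, so it cannot have determined a sample that does not yet exist. If the term only means that power was worked out once feasibility had fixed the number, then power did not determine the number, and its inputs are still missing.

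**The comparison apparently powered is not carried through the plan.** With 10 SHI and 10 SDI, the natural reading of a difference in dip is SHI v SDI. That comparison is one of the three parts of the primary objective, yet no hypothesis states it and no analysis is explicitly assigned to it.

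At stake is how the dip result will be read. A null finding could be defended by an 80% power that nobody can check. The type comparison could also end up resting on a by-product of an ANOVA that may not account for two implants sharing a patient.

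**Working it through.** **Inputs.** From the protocol: 10 SHI and 10 SDI in 10 participants, difference 5 ISQ, alpha 0.05, power 80%, at least 80% split-mouth. Assumptions: two-sided testing; all SDs and within-patient correlations; 8 pairs as the reading of 80% of 10 participants.

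**Can the 80% be reproduced?** Not without an SD and a test. It can only be solved backwards. Power is the probability that a non-central t with df degrees of freedom and non-centrality 5/(SD × f) exceeds t(0.975, df) in absolute value. The 95% CI half-width is t(0.975, df) × SD × f.

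- Independent, 10 v 10: f = √(2/10) = 0.447, df 18, t = 2.101
- 10 pairs: f = √(1/10) = 0.316, df 9, t = 2.262
- 8 pairs: f = √(1/8) = 0.354, df 7, t = 2.365

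For pairs, SD means the SD of the within-patient difference, which is per-implant SD × √(2(1 − correlation)).

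| Layout | Largest SD giving 80% | Power at SD 3, 4, 5, 6 | Half-width (ISQ) at SD 3, 4, 5, 6 |
|---|---|---|---|
| Independent | 3.77 | 94, 75, 56, 42% | 2.8, 3.8, 4.7, 5.6 |
| 10 pairs | 5.02 | >99, 94, 80, 65% | 2.1, 2.9, 3.6, 4.3 |
| 8 pairs | 4.33 | 98, 86, 68, 53% | 2.5, 3.3, 4.2, 5.0 |

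Example: independent at SD 5 gives 2.101 × 5 × 0.447 = 4.7. One-sided, the limits become 4.32, 5.86 and 5.11. The 80% is therefore attainable, but it depends wholly on unstated inputs.

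**Which analysis covers SHI v SDI dip magnitude?**

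| Section 9 analysis | Assigned to | Covers the dip contrast? |
|---|---|---|
| Paired and independent t-tests | Primary stability (H_01) | No |
| Correlation | Baseline ISQ and dip (H_02) | No, not a comparison of types |
| Linear mixed models | ISQ over time | Related dynamics, but not T0 minus each implant's own minimum |
| Two-way ANOVA | Type-by-density interaction on dip (H_03) | A type main effect as by-product; no patient term stated |

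**What if the ANOVA ignores pairing?** An unpaired t-test on all 20 implants stands in for its type effect, compared with a paired t-test on the complete pairs. The true difference is 5 ISQ, per-implant SD is 4 or 5, and there are 400,000 simulated normal data sets per case. The second layout assumes 8 pairs plus one patient with two SHI and one with two SDI.

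| Layout | Correlation | Unpaired type I error | Power at SD 4, unpaired v paired | Power at SD 5, unpaired v paired |
|---|---|---|---|---|
| 10 pairs | 0 | 5.0% | 75 v 70% | 56 v 51% |
| 10 pairs | 0.3 | 2.3% | 79 v 84% | 57 v 66% |
| 10 pairs | 0.5 | 1.0% | 82 v 94% | 58 v 80% |
| 8 pairs + 2 patients | 0.3 | 3.2–3.3% | 77 v 73% | 57 v 54% |
| 8 pairs + 2 patients | 0.5 | 2.2% | 79 v 86% | 59 v 68% |

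Ignoring pairing makes the type comparison conservative in every case with positive correlation. The power cost is largest with ten complete pairs. With 8 pairs and correlation 0.3, the paired test on pairs alone has less power than the unpaired test, because it discards four implants.

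**The case against.** The strongest defence is that this is a small pilot whose size was set first by eligibility. Power is only the second ground, and post-hoc may be a slip for a priori. An SD, test and sidedness could also sit in a statistical analysis plan that is not shown. This lowers the weight of the point. It does not rescue a sentence that lets a post-hoc analysis determine a prospective sample, and a later plan would not change that sentence.

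A second defence is that the mixed models on ISQ trajectories could include a patient random effect and so respect pairing for the early stability dynamics. This stands, and it would be wrong to say that the plan has no analysis able to handle pairing. Those models are not tied to the Section 8 dip magnitude, however, and no hypothesis is attached to them.

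A third is that the protocol does not say the ANOVA lacks a patient term. That also stands. An ordinary between-implant ANOVA is the likely reading, but it is an inference.

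**Conclusion.** The point holds as a correction to the text and to the analysis. The 80% power has no stated basis and is described in a way that cannot apply to a future sample. One part of the primary objective, the SHI v SDI dip contrast, has no hypothesis and no explicitly assigned test.

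The claimed power is met only up to an SD of 3.77 (independent), or an SD of differences of 5.02 (10 pairs) or 4.33 (8 pairs), at two-sided 0.05. If the ANOVA ignores pairing, true type I error is about 2.3% to 1.0% with ten pairs and about 3.2% to 2.2% with 8 pairs plus two same-type patients, at assumed correlations of 0.3 to 0.5.

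Four stronger readings are not supported:

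- **The 80% is wrong or the sample too small.** No SD is given, and 80% is attainable.
- **The data were already collected.** Nothing beyond the word post-hoc suggests it, and Section 5 uses the future tense.
- **Ignoring pairs inflates false positives.** In the layouts examined the error is conservative.
- **A paired t-test is the obvious remedy.** With 8 pairs it can lose power, so all implants should be used.

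That Section 5 means SHI v SDI is the natural reading, not a stated fact, since Section 8 defines the dip within one implant.

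**What to change.** **Section 5.** Delete the post-hoc power claim. Justify ten participants as a pilot by eligibility and precision, giving the 95% CI half-widths above over a range of assumed SDs for paired and independent layouts. Alternatively, replace the claim with an a priori calculation that states a sourced SD, the number of pairs, sidedness, alpha and the test, and names the contrast.

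**Section 2.** Add the SHI v SDI difference in dip magnitude as a hypothesis.

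**Section 9.** Analyse dip magnitude over all 20 implants by a mixed model with a patient random effect and fixed effects for implant type and bone density, which Section 8 treats as a primary covariate. Include their interaction to test H_03, in place of the ANOVA. Name a small-sample degrees-of-freedom method, such as Kenward–Roger or Satterthwaite, because there are only ten patients. Report the type difference with its 95% CI against the plan's own 5-ISQ threshold.

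**Cost.** No extra patients or visits. The stated 80% power is lost or becomes less favourable, and one hypothesis is added.
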